8.5 Extent of Exposure

8.5.1 Duration of Study Drug Exposure

Duration of study drug exposure (in days) will be calculated as date of last study medication exposure minus date of first study medication administration + 1 day, regardless of study drug interruption. Details of study drug exposure derivation is described in Section 7.1.

Study drug exposure will be summarised by treatment group and separated for the double blind and open label phase on the SAF population using time intervals and summary statistics. Planned and actual dose as well as injections at all sites per subject and treatment cycle will be listed.

Due to the COVID-19 pandemic and the treatment hold, the duration of study drug exposure will be also derived as described above but excluding the days between the end of cycle visit and the re-treatment visit between each cycle. This will be summarized using summary statistics.

8.5.2 Treatment Compliance

All study procedures are to be performed under supervision at the study site, and thus, no separate procedures will be used to monitor subject compliance.

8.6 Efficacy Analyses

8.6.1 Analysis Methods

The analyses of the primary and secondary outcome measures will be based on different statistical tests such as Cochran-Mantel-Haenszel (CMH) test, Pearson Chi-Square test, Wilcoxon Rank Sum test and Fisher's exact test, if appropriate. Details for each efficacy endpoint will be provided in the following sections. Subgroup analyses will be described in Section 8.8.1.

8.6.1.1 Multiplicity

The testing of the primary and the key secondary efficacy endpoints will be performed with appropriate multiplicity control based on the FAS population. The results of each test will only be considered confirmative if the previous test in the order showed a confirmatory result at a one-sided significance level of 0.025. If the one-sided p-value is larger than 0.025 for

Statistical Analysis Plan (SAP)

CROMA
est. 1976

any of the tests, the results of the subsequent tests will only be considered exploratory, and not confirmatory. The application of this hierarchical approach keeps the global significance level to 0.025 one-sided and requires no further adjustment of the significance level.

The following order of tests will be applied:

- Primary endpoint (composite endpoint)
- Key secondary endpoint 1
 - 1.1: The modified Skindex-16 (GL-QoL) Emotional domain
 - 1.2: The modified Skindex-16 (GL-QoL) Social Functioning domain
 - 1.3: The modified Skindex-16 (GL-QoL) Overall score
 - 1.4: The FACE-Q Appraisal of Lines Between Eyebrows scale
 - 1.5: The FACE-Q Age Appraisal VAS score

All other analyses (e.g., additional analyses of the primary and the key secondary efficacy endpoints using other analysis populations or other statistical methods, analyses of additional secondary endpoints) will only be considered exploratory.

8.6.1.2 Treatment by Center Interaction Analysis (multi-center study)

Treatment-by-center interaction will be tested using the Breslow-Day test for homogeneity of the odds ratios for the primary efficacy endpoint.

8.6.2 Analysis of Primary Efficacy Endpoint

Primary Analysis:

The proportion of subjects (responders) meeting the primary endpoint with a FWS score of 0 or 1 and an improvement ≥ 2 points in FWS score (at maximum frown) at week 4 visit relative to baseline, based on both the investigator and the subject in-clinic assessments will be analyzed using the CMH test (with stratification variable site; small sites with less than 3 placebo subjects will be combined) using a significance level (α) of 0.025. The null hypothesis H_0 given below will be tested against the alternative hypothesis H_1 :

$$H_0: p_{BoNT/A-DP} \leq p_{Placebo}$$

$$H_1: p_{BoNT/A-DP} > p_{Placebo}$$

The CMH test will be applied by the SAS procedure Proc Freq using the General Association Statistic. The one-sided p-value will be derived by halving the two-sided p-value produced by the SAS procedure. Superiority of BoNT/A-DP over placebo will only be concluded if, besides statistical significance (one-sided p-value ≤ 0.025), the proportion of responders in the BoNT/A-DP treatment group is higher than for the placebo treatment group.

Statistical Analysis Plan (SAP)

CROMA
est. 1976

The FAS population will serve as the primary analysis set.

Subjects with missing investigator or subject in-clinic assessments with the FWS at baseline or visit week 4 will be assigned as being non-responders.

Additional Exploratory Analyses on the Primary Efficacy Endpoint Variable:

Further analyses on the primary efficacy endpoint variable are exploratory. A one-sided Pearson χ^2 -test will be applied. Two-sided CI of 95% for the responder rates in the BoNT/A-DP and the placebo treatment groups will be calculated using Wilson scores. As a sensitivity analysis for the primary efficacy endpoint, a tipping point analysis will be performed. Each missing value will be assigned to either a response or non-response, so that all possible combinations of replacing one or more missing values within each treatment group will be analyzed. P-values will be calculated for each combination and graphically displayed using a scatter plot. These analyses will be performed using the FAS population.

The CIs will also be calculated for the additional analyses as listed in the following:

- The primary efficacy endpoint measure using the observed values only, i.e., missing investigator or the subject in-clinic assessments with the FWS at baseline or week 4 visit will be excluded from analysis but not assigned as being non-responders. This analysis will be performed for the FAS, MFAS and PP populations.
- The primary efficacy endpoint measure using the MFAS and PP populations.
- The primary efficacy endpoint measure applying the LOCF for week 4 visit. This analysis will be done for FAS, MFAS and PP populations.

8.6.3 Analysis of Secondary Efficacy Endpoints

The following order of tests will be defined for the analysis of the key secondary efficacy endpoint with multiplicity control as described in 8.6.1.1:

- Primary endpoint (composite endpoint)
- Key secondary endpoint 1
 - 1.1: The modified Skindex-16 (GL-QoL) Emotional domain
 - 1.2: The modified Skindex-16 (GL-QoL) Social Functioning domain
 - 1.3: The modified Skindex-16 (GL-QoL) Overall score
 - 1.4: The FACE-Q Appraisal of Lines Between Eyebrows scale
 - 1.5: The FACE-Q Age Appraisal VAS score

Analysis of key secondary efficacy endpoint 1: The extent of change in psychological impact (emotional and social functioning, and concerns relating to glabellar lines) at week 4 after

Statistical Analysis Plan (SAP)

CROMA
est. 1976

the first treatment, in the BoNT/A-DP group in comparison with placebo, relative to baseline, as assessed by the modified Skindex-16 (GL-QoL) and the FACE-Q Appraisal of Lines Between Eyebrows and FACE-Q Age Appraisal VAS.

The modified Skindex-16 (GL-QoL) and FACE-Q Appraisal of Lines Between Eyebrows scale and FACE-Q Age Appraisal VAS scales will be analyzed according to the foreseen analysis approach of these tools, as described below.

Emotional and Social Functioning

The modified Skindex-16 (GL-QoL) Emotional and Social Functioning domains and overall scores will be derived in accordance with the Skindex-16 manual, adapted for the GL-QoL. The scores will be standardized on a scale from 0 (no impact) to 100 (maximal impact); a scale score is the average of responses to items addressing a construct. Domain and overall scores will be calculated if at least two of three social and if at least two of four emotional domain items are present. Derivation details are included in Appendix B. The absolute change from baseline (measured on the screening visit) will be calculated for the domain and overall scores and statistically compared between the treatment groups using the Wilcoxon Rank Sum test or t-test, if appropriate. Estimates of ‘mild’, ‘moderate’, and ‘severe’ psychological impact, and of the minimal clinical important difference, will be used to aid interpretation of scores and will be considered exploratory.

The analysis will be conducted with respect to the hierarchical order of the key secondary efficacy endpoint; the analysis using the Emotional domain first, the Social Functioning domain second, and the overall score third. All analyses will be conducted on observed values only, i.e., missing domain and overall scores will be excluded from analysis; no imputation of missing domain and overall scores will be performed.

Concerns Relating to Glabellar Lines

The FACE-Q Appraisal of Lines Between Eyebrows scale and FACE-Q Age Appraisal VAS scores will be derived in accordance with the developers’ instructions and missing data treated accordingly. The absolute change from baseline (measured on the screening visit) will be calculated for the FACE-Q Appraisal of Lines Between Eyebrows scale and for the FACE-Q Age Appraisal VAS score and statistically compared between the treatment groups using the Wilcoxon Rank Sum test. All analyses will be conducted on observed values only, i.e., missing scale scores will be excluded from analysis; no imputation of missing scores will be performed. This analysis will be conducted with respect to the hierarchical order of key secondary efficacy endpoints as well; the analysis of FACE-Q Appraisal of Lines Between Eyebrows scale first, followed by the analysis of FACE-Q Age Appraisal VAS scores.

Statistical Analysis Plan (SAP)

CROMA
est. 1976

Exploratory Analyses

Exploratory analyses of modified Skindex-16 (GL-QoL) domain and overall score and FACE-Q Appraisal of Lines Between Eyebrows scale and FACE-Q Age Appraisal VAS will also be conducted using the MFAS and PP populations. The analyses described in the two previous sections will be repeated for these populations.

In addition, shift tables tables will be produced displaying the Psychological Impact of Modified Skindex-16 (GLQoL) at baseline versus week 4. The FAS, MFAS and PP populations will be used.

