12.4.2 Secondary Outcome Measures

Key Secondary Analyses:

The testing of the key secondary endpoint will be performed with appropriate multiplicity control based on the FAS population. The results of each test result will only be considered confirmative if the previous test in the order showed a confirmatory result at a one-sided significance level of 0.025. If the one-sided p-value is larger than 0.025 for any of the tests, the results of the subsequent tests will only be considered exploratory, and not confirmatory. The application of this hierarchical approach keeps the global significance level to 0.025 one-sided and requires no further adjustment of the significance level.

The following order of tests will be defined:

- Primary endpoint (composite endpoint)
- Key secondary endpoint 1
 - 1.1: The modified Skindex-16 (GL-QoL) Emotional domain
 - 1.2: The modified Skindex-16 (GL-QoL) Social Functioning domain
 - 1.3: The modified Skindex-16 (GL-QoL) Overall score
 - 1.4: The FACE-Q Appraisal of Lines Between Eyebrows scale
 - 1.5: The FACE-Q Age Appraisal VAS score

Analysis of key secondary endpoint 1: The extent of change in psychological impact (emotional and social functioning, and concerns relating to glabellar lines) at week 4 after the first treatment, in the BoNT/A-DP group in comparison with placebo, relative to baseline, as assessed by the modified Skindex-16 (GL-QoL) and the FACE-Q Appraisal of Lines Between Eyebrows and FACE-Q Age Appraisal VAS.

The modified Skindex-16 (GL-QoL) and FACE-Q Appraisal of Lines Between Eyebrows scale and FACE-Q Age Appraisal VAS will be analyzed according to the foreseen analysis approach of these tools, as described below.

Emotional and Social Functioning

The modified Skindex-16 (GL-QoL) Emotional and Social Functioning domains and overall scores will be derived in accordance with the Skindex-16 manual, adapted for the GL-QoL. The scores will be standardized on a scale from 0 (no impact) to 100 (maximal impact); a scale score is the average of responses to items addressing a construct. Domain and overall scores will be calculated if at least two of three social and of at least two of four emotional domain items are present. The absolute change from baseline (measured on the screening visit) will be calculated for the domain and overall scores and statistically compared between the treatment groups using the Wilcoxon Rank Sum test (or t-test). Estimates of 'mild',

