3.2 Randomization and Blinding

3.2.1 Randomization

This is a randomized, double blind, placebo-controlled efficacy and safety clinical study followed by an open label extension. Subjects will be randomly assigned to receive either BoNT/A-DP or placebo at a ratio of 3:1 respectively in the first treatment cycle. The 3:1 ratio in favor of active treatment versus placebo has been selected to increase the safety database size.

Randomization will be performed per study site via interactive web response system (IWRS). One unique randomization code will be assigned to each subject.

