5 SAMPLE SIZE AND POWER

The primary efficacy endpoint is a composite endpoint comprising investigator and subject assessments of treatment effectiveness using the FWS. Composite endpoint treatment success (CETS) is defined as ≥ 2 point reduction in FWS score at maximum frown achieving a score of 0 or 1 at the visit week 4 relative to baseline based on investigator assessment and subject assessment. Thus, a subject is a CETS “Responder” only if both investigator- and subject-rated success criteria are satisfied at the visit 4 weeks after baseline.

The primary analysis of efficacy is the proportion of responders in the BoNT/A-DP treatment group compared with the placebo treatment group. For superiority testing of BoNT/A-DP compared with placebo, the following assumptions for the sample size calculation will be used:

Item	Assumption	Comments
Underlying test	Fisher's Exact Test	Standard test for a response parameter for small numbers
Randomization scheme (BoNT/A-DP: Placebo)	3:1	More active treatment subjects to enlarge safety database
Power $1-\beta$	90%	Actual power is 92.3%
Significance level (α)	0.025 one-sided	
Response Arm BoNT/A-DP	46%	Conservative value based on the results of previous studies (BLESS I and BLESS II)
Response Arm Placebo	2%	Conservative value based on the results of previous studies (BLESS I and BLESS II)
Software		The sample size calculation was performed using the software nQuery Advisor [®] 8.2.1.0

Statistical Analysis Plan (SAP)

CROMA
est. 1976

Based on these assumptions, 39 subjects in the BoNT/A-DP arm and 13 subjects in the placebo arm are required, i.e., 52 subjects in total. This is a very small sample size and not sufficient for a detailed evaluation of the data, including subgroup analyses. Furthermore, the response rate could not be estimated with sufficient precision. Assuming a response rate of 46% in the BoNT/A-DP group, a two-sided confidence interval (CI) of 95% with a distance from the response rate to the CI limits of about 5.6% could be achieved with a sample size of 225 subjects in the BoNT/A-DP group. A 3:1 randomization of BoNT/A-DP (225 subjects) to placebo (75 subjects) is proposed, which is adequate for a precise estimate of response rate and for post-hoc sensitivity analyses (i.e., treatment-by-center and other subgroup analyses), also taking into account a drop-out rate.

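### The five confirmatory key secondary tests have no site stratum and no baseline covariate, and for the three GL-QoL scores the choice of test is left open

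*SAP*

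**What the plan says.** SAP 8.6.1.1 puts the primary endpoint and then five key secondary tests in a fixed order. Each counts as confirmatory only if the one before it "showed a confirmatory result at a one-sided significance level of 0.025". Tests 1.1 to 1.3 are the GL-QoL Emotional, Social Functioning and Overall scores. Tests 1.4 and 1.5 are the FACE-Q Appraisal of Lines Between Eyebrows scale and the Age Appraisal VAS.

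For 1.1 to 1.3, SAP 8.6.3 says that change from the screening score will be "statistically compared between the treatment groups using the Wilcoxon Rank Sum test or t-test, if appropriate". Protocol 12.4.2 has "statistically compared between the treatment groups using the Wilcoxon Rank Sum test (or t-test", with nothing further in the bracket. Neither document says what would make the t-test appropriate. For 1.4 and 1.5 both documents name the Wilcoxon test alone.

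On randomisation, SAP 3.2.1 says: "Randomization will be performed per study site via interactive web response system (IWRS". The primary CMH test (SAP 8.6.2) is stratified by site, and sites with fewer than three placebo subjects are pooled. SAP 8.6.3 gives no stratum and no covariate for any of the five key secondary tests. Baseline enters only by subtraction.

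The protocol synopsis, under its key secondary analysis, says that the analyses described for the primary endpoint will be repeated. Read literally, that is a site-stratified CMH test, which is not what Protocol 12.4.2 or SAP 8.6.3 describes.

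**The concern.** Three things are at stake.

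- **Precision.** The scores are bounded, and a subject can improve only as far as the screening score allows. Entry needs a score above zero on either the Emotional or the Social Functioning subscale, so a subject can enter with zero on the other one and have no room to improve there. Screening score and site are both known before treatment, and neither is used to reduce variance. In a fixed sequence, one missed test ends every later confirmatory claim.
- **An open test.** Tests 1.4 and 1.5 can be confirmatory only if 1.1 to 1.3 all succeed. With two tests on offer and no rule, the documents do not themselves secure the 0.025 level that SAP 8.6.1.1 claims.
- **No named estimate.** SAP 4.2 defines the endpoint as how much psychological impact changes relative to placebo. SAP 8.6.3 names tests but no between-group difference.

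**Working it through.** **The plan's own figure.** SAP 5 states 92.3% power for the primary comparison: "Fisher's Exact Test", one-sided 0.025, 46% against 2%, 39 against 13 subjects. Exact enumeration gives 92.27%, so it reproduces; 36 against 12 gives 87.6%. The enrolment of 353 is 300 / (1 − 0.15). These figures concern the primary endpoint only. No power, effect, SD or correlation is given for any key secondary test, so the values of ρ, effect and site share below are assumptions.

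**Baseline adjustment.** Assume equal variance σ² at screening and week 4, with correlation ρ.

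- Variance of a change score: 2(1 − ρ)σ².
- Residual variance under ANCOVA: (1 − ρ²)σ².
- Ratio: (1 − ρ²) / [2(1 − ρ)] = (1 + ρ)/2.

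With the 225 and 75 of SAP 5, √(1/225 + 1/75) = 0.1333. Power is Φ(0.35 / (0.1333 s) − 1.96) for an assumed effect of 0.35 SD, where s = √[2(1 − ρ)] for the change score and √(1 − ρ²) for ANCOVA. The difference detectable with 90% power is (1.96 + 1.28) × 0.1333 × s = 0.432 s.

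| ρ | Variance ratio | Power, change score | Power, ANCOVA | Detectable, change score | Detectable, ANCOVA |
|---|---|---|---|---|---|
| 0.3 | 0.65 | 60% | 79% | 0.51 SD | 0.41 SD |
| 0.5 | 0.75 | 75% | 86% | 0.43 SD | 0.37 SD |
| 0.7 | 0.85 | 92% | 96% | 0.33 SD | 0.31 SD |

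This comparison is with a mean change score. The planned Wilcoxon test needs a separate check. In a simulation with floor-limited discrete scores (225 against 75, 0.35 SD shift before flooring, site accounting for 5% of variance), ANCOVA with site and baseline had power 74%, 80% and 92% at ρ = 0.3, 0.5 and 0.7. The Wilcoxon test on change had 48%, 60% and 78%.

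**Type I error.** Null simulation: seven sites, 3:1 within site, 225 against 75, ρ = 0.5, 20,000 runs per row. The entries are one-sided rejection rates at 0.025. The Monte Carlo standard error is √(0.025 × 0.975 / 20,000) = 0.0011.

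| Site share | Scores | Wilcoxon | t-test | Smaller p | Normality pretest | van Elteren | ANCOVA |
|---|---|---|---|---|---|---|---|
| 0 | normal | 0.0243 | 0.0246 | 0.0296 | 0.0253 | 0.0247 | 0.0256 |
| 0 | skewed | 0.0244 | 0.0246 | 0.0312 | 0.0245 | 0.0250 | 0.0268 |
| 5% | skewed | 0.0226 | 0.0226 | 0.0286 | 0.0223 | 0.0250 | 0.0272 |
| 15% | normal | 0.0186 | 0.0190 | 0.0228 | 0.0193 | 0.0250 | 0.0256 |
| 15% | skewed | 0.0189 | 0.0194 | 0.0242 | 0.0192 | 0.0254 | 0.0269 |

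The unstratified tests are at or below nominal throughout. Taking the smaller p-value exceeds 0.025 when the site share is 0 or 5%, but not at 15%. A choice fixed by a normality pretest stays at about 0.025 or below. ANCOVA with skewed scores runs up to about two standard errors above nominal.

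**The case against.** **The alpha figure is a worst case.** It needs both tests run on unblinded data and the smaller p-value kept, and no document plans that. Wilcoxon is named first, Protocol 12.5 requires the SAP to be final before database lock and/or unblinding, and a blinded data review comes before unblinding. This stands as a limit on the claim. It does not close the gap, because the review in SAP 6.6 and 8.9 covers deviations and analysis sets, not the choice of test.

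**ANCOVA over Wilcoxon may be only a preference.** The (1 + ρ)/2 ratio does not carry over to a rank test, and examples exist where the rank test wins. With a normal baseline and an unbounded heavy-tailed change (correlation about 0.72), one simulation gave 91% power for Wilcoxon on change and 35% for ANCOVA. The caution about the ratio is right. The example, however, does not resemble these bounded scores, and the floor-limited simulation points the other way. Since the true distribution is not given, a rank-based sensitivity analysis is worth having.

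**Site is examined elsewhere.** SAP 8.8.1 has site and country subgroup analyses of the key secondary endpoint. SAP 8.6.1.1 makes such additional analyses exploratory, so they do not change the confirmatory tests.

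**Effect sizes are not wholly absent.** SAP 8.1 gives descriptive statistics by group and 95% CIs where relevant, and SAP 8.6.3 adds shift tables and minimal-important-difference estimates. The fair statement is that no between-group estimator is named, not that no estimate could be reported.

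**Conclusion.** The point holds as a gain in precision available at little cost, plus an unclosed choice of test for 1.1 to 1.3. The assumed correlations of 0.3 to 0.7 put the variance reduction at about 35% to 15% against a mean change score. The open choice could take one-sided alpha to about 0.03, but only if made after unblinding by the smaller p-value and with small site effects.

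A reader might infer more, and the documents do not support it:

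- *That all five tests are open.* Tests 1.4 and 1.5 are fixed to Wilcoxon in both documents.
- *That baseline is ignored.* The endpoint is change from the screening score; what is missing is covariate adjustment.
- *That leaving out site invalidates the tests.* It makes them conservative, at about 0.019 with a 15% site share.
- *That the sequence is underpowered.* With no SD, effect or correlation stated, this cannot be shown; the power figures above are illustrations.

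How missing scores are handled is a separate question and not part of this point.

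**What to change.** In SAP 8.6.3, delete the t-test alternative and specify one method for all five scores: ANCOVA on week-4 change with treatment, site (pooled as for the primary CMH test) and screening score. Report the adjusted treatment difference with its 95% CI. Make the site-stratified Wilcoxon (van Elteren) test the sensitivity analysis. Fix this before the unblinding for the interim analysis, because SAP 8.9 makes that the final analysis of the key secondary endpoint. Reconcile the synopsis sentence with Protocol 12.4.2 and SAP 8.6.3.

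The cost is wording and programming, with no new data. A subject without a screening score already has no change score, so the covariate excludes nobody further. The price is a linear-model assumption and, in the skewed simulations, a rejection rate of about 0.027; the van Elteren test, at 0.025, is the check on both.
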